Behavioral profile consistent with a VS or MCS as assessed with the Coma Recovery Scale Revised.

Chronic patients

> 3 months post injury for non-traumatic injuries, >12 months post-injury for traumatic injuries

Behavioral profile consistent with a VS or MCS as assessed with the Coma Recovery Scale Revised.

Exclusion Criteria (all patients):

deep sedation

history of neurological illness prior to injury

inability to safely enter the MR environment (e.g., ferromagnetic non MR safe implants)

Neurobehavioral Assessment Procedure

Neurobehavioral assessments will be conducted using the Coma Recovery Scale Revised (CRS-R).¹⁹ Baseline responsiveness will be assessed prior to LIFUP exposure. Responsiveness will also be assessed immediately following, as well as on the days following each LIFUP exposure. The Coma Recovery Scale – Revised, is a standard clinical protocol used to assess a patient's level of consciousness. This test allows us to assess your level of response to sensory stimulation, ability to understand language and to communicate. This procedure is typically administered at bedside. This testing should take 25 minutes.

In addition, the Glasgow Outcome Scale extended score will be assessed to evaluate outcome at protocol end and follow-up

Paramedical Measurements

- (1) Clinical EEG: data from the clinical recordings will be collected.
- (2) MR acquisition (performed in MR suite):
 - (A) Structural MRI acquisition:
 - (i) T1-weighted (MPRAGE)
 - (ii) Diffusion Tensor Imaging (DTI)
 - (B) Functional MRI acquisition:
 - (ii) Resting state task (BOLD, during sonication)

Electroencephalography (EEG) is a widely employed technique that measures electrical brain activity. In order to acquire EEG data we will fit you with a small elastic cap that you will wear on your head. This procedure (expected duration: 10 minutes + set-up time, up to 20 minutes) will allow us to measure electrical brain activity as you rest. This procedure is entirely non-invasive.

Magnetic Resonance Imaging (MRI) is a widely used method to assess body tissues, including the brain, in a non-invasive manner. In the context of this study, MRI will be used to assess brain structure and function (in response to LIFU). MRI protocols include T1 MPRAGE, Diffusion Tensor Imaging (DTI), and T2* BOLD sequences.

Procedure

The temporal sequence of events, for each cycle, is as follows:

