- Clinical EEG (baseline): 10 min of EEG data, from the clinical recordings, will be collected for analysis
- Baseline clinical measures collection (25 min)
- Baseline fMRI measures collection (in MRI suite; 30 min+20 min set-up)
- Administration of LIFUP (in MRI suite; 10 min + 20 min set-up)
- Post-LIFUP fMRI measures collection (in MRI suite; 30 min)
- Post-LIFUP clinical measures collection (25 min)
- Clinical EEG (post-LIFUP): 10 min of EEG data, from the clinical recordings, will be collected for analysis

LIFU Procedure. The area surrounding the planned LIFU entry point on the head will be shaved prior to positioning in order to minimize the impedance of ultrasound due to air bubbles. Ultrasound gel (aquasonic) will be first applied to this region and smoothed in order to remove air pockets. The ultrasound transducer will then be positioned so that its center lay on the squamous portion of the temporal bone (the thinnest part of the human skull) in order to minimize ultrasound scatter and refraction through the bone. A thin layer of gel will be applied to the surface of the transducer, and bubbles will be similarly smoothed from this layer. The transducer will then be coupled to the head with gel filling any open space between the transducer membrane and the scalp with two straps—one horizontal and one vertical—securing the device to the patient. Conventional soft foam padding and pillows will be used to further secure the positioning of the device and decrease the potential for head motion during the procedure. Next, we will acquire a rapid (95 s) T1-weighted MPRAGE anatomical image. Using a circular MR fiducial and the visible center of the transducer, reference lines will be drawn in the transverse and coronal planes, using the Siemens 3D display GUI available as part of the MRI device's console software to visually locate the target of the LIFU beam

in three dimensions. Adjustments to the positioning of the transducer on the head will be made iteratively, re-acquiring a T1-weighted MPRAGE at each iteration, until the beam trajectory from the center of the transducer is assessed to be in-line with the intended target.

Statistical Plan and Analysis

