- **Structural MRI – Diffusion Tensor Imaging (DTI).** The aim of this analysis is to assess any changes, in terms of structural connectivity, and in particular thalamo-frontal connectivity, induced

by the LIFUP stimulation. Data will be first preprocessed following standard pipelines in the field (Behrens et al., 2003b); then, streamlines from thalamus to the whole brain will be calculated, for every subject individually, between thalamus and cortex (Behrens et al., 2003a). The streamlines will then be entered, the dependent variable, in the group analysis (i.e., the mixed-design ANCOVA). This analysis is a direct test of whether thalamo-cortical connectivity is affected (as the mesocircuit hypothesis predicts) by our intervention.

- **Electroencephalography.** This analysis is aimed at assessing whether LIFUP session alters the spectral profile of electroencephalographic recordings (EEG). Indeed, it is known that patients at different levels of consciousness after severe brain injury exhibit different electrocortical patterns (e.g., patients with severe disorder of consciousness exhibit large "delta" -- that is: slow -- waves of activity, as compared to the more rapid "alpha" waves typically seen in healthy individuals). Data will be preprocessed following previous literature (Lechinger et al., 2013), then for each channel we will derive a characterization of each patient's spectral profile. This information will then be entered in the group analysis.

1. Monti MM. Ethics, Neuroimaging and Disorders of Consciousness: What Is the Question? *AJOB Neuroscience*. 2013;4(4):1-2.
3. Monti MM. Cognition in the vegetative state. *Annu Rev Clin Psychol*. 2012;8:431-54. Epub 2012/01/10. doi: 10.1146/annurev-clinpsy-032511-143050. PubMed PMID: 22224835.
4. Jennett B. Thirty years of the vegetative state: clinical, ethical and legal problems. *Prog Brain Res*. 2005;150:537-43. Epub 2005/09/28. doi: 10.1016/S0079-6123(05)50037-2. PubMed PMID: 16186047.

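### The baseline EEG comes before the CRS-R and the post-LIFUP EEG after it, so the supplementary pre/post spectral comparison may be confounded by the preceding behavioural testing

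*Combined protocol and SAP*

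**What the plan says.** The Procedure section introduces its list with "The temporal sequence of events, for each cycle, is as follows", so the order is prescribed. The first step is "Clinical EEG (baseline): 10 min of EEG data, from the clinical recordings, will be collected for analysis". Then come baseline clinical measures (25 min), baseline fMRI, LIFUP, post-LIFUP fMRI and post-LIFUP clinical measures (25 min). The final step is "Clinical EEG (post-LIFUP): 10 min of EEG data, from the clinical recordings, will be collected for analysis".

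The clinical measures are not named in that list. The Neurobehavioral Assessment Procedure section gives the CRS-R the same 25 min duration, and no other battery of that length is described. Of the CRS-R that section says: "This test allows us to assess your level of response to sensory stimulation, ability to understand language and to communicate". The Paramedical Measurements section describes the EEG as a recording at rest and allows for set-up time.

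The Electroencephalography item of the Statistical Plan and Analysis states the purpose: "This analysis is aimed at assessing whether LIFUP session alters the spectral profile of electroencephalographic recordings (EEG"). It cites slow delta against faster alpha activity as distinguishing levels of consciousness, and says that each patient's spectral profile goes into the group analysis. It mentions no washout, no rule for choosing the segment, and no term for what the patient was doing beforehand.

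**The concern.** The steps form a mirror image around LIFUP. That looks symmetrical, but it means the two EEGs are not taken under matched conditions: one precedes a block of sensory and language stimulation and the other follows one. Arousal produced by the testing, or fatigue after it, could plausibly move the balance of slow and fast activity, which is the quantity the analysis reads.

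The difference in order is the same in every patient and every cycle. If testing shifts the later spectrum on average, a larger sample estimates the mixture of that shift and any LIFUP effect more precisely, but does not separate them. A move from delta towards alpha could be credited to LIFUP when it is not due to LIFUP, or a real move could be masked.

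**Working it through.** The plan states no figure for this point (no EEG effect size, sample size or interval), so the check is a timeline and a decomposition of the comparison.

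**Inputs** (Procedure section): EEG 10 min; clinical measures 25 min; baseline fMRI 30 + 20 set-up = 50 min; LIFUP 20 set-up + 10 = 30 min; post-LIFUP fMRI 30 min; clinical measures 25 min; EEG 10 min. Assumptions: no transport time, and EEG set-up before the second recording of 0 to 20 min. The wording on set-up in Paramedical Measurements is ambiguous, so the whole range is shown.

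**Plan as written**

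- End of post-LIFUP CRS-R to start of post-LIFUP EEG: 0 + (0 to 20) = 0 to 20 min.
- End of LIFUP to start of post-LIFUP EEG: 30 + 25 + (0 to 20) = 55 to 75 min.
- End of baseline EEG to start of post-LIFUP EEG: 25 + 50 + 30 + 30 + 25 + (0 to 20) = 160 to 180 min.
- Before the baseline EEG, no CRS-R is listed within the cycle.

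**Decomposition.** Let L be the mean spectral change due to LIFUP, c(g) the mean shift left by a CRS-R that ended g minutes earlier, and T the mean effect of everything else that differs between the recordings (scanning, elapsed time). As written,

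E[post − baseline] = L + c(g_post) + T, with g_post of 0 to 20 min.

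Only the sum is estimable. The documents give no value, sign or duration for c.

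**Baseline segment moved to after the baseline CRS-R**

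E[post − baseline] = L + [c(g_post) − c(g_base)] + T.

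The bracket is zero if g_post = g_base and the testing leaves the same shift on both occasions. T remains:

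- End of baseline EEG to start of post-LIFUP EEG: 50 + 30 + 30 + 25 + (0 to 20) = 135 to 155 min, still more than two hours.
- End of LIFUP to start of post-LIFUP CRS-R: 30 min, unchanged.
- End of LIFUP to start of post-LIFUP EEG: 55 to 75 min, unchanged.

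**Post-LIFUP EEG moved to before the post-LIFUP CRS-R, for comparison**

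- End of LIFUP to start of post-LIFUP EEG: 30 + (0 to 20) = 30 to 50 min.
- End of LIFUP to start of post-LIFUP CRS-R: 30 + (0 to 20) + 10 = 40 to 60 min, that is, 10 to 30 min later than planned.
- End of baseline CRS-R to start of post-LIFUP EEG: 50 + 30 + 30 + (0 to 20) = 110 to 130 min.

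**The case against.** Several things can be said for leaving the plan alone.

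*No carry-over is demonstrated.* A reader might infer that the spectral change does contain an effect of testing. The documents do not support that: nothing in them shows that a CRS-R alters a later resting spectrum, in which direction, or for how long. If it aroused some patients and tired others with no net shift, it would add noise and not bias. This stands, and limits the point to possible confounding.

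*The gap is unknown.* A reader might also infer that the EEG starts the moment testing ends. The list gives an order, not intervals. Set-up time, or a later segment of the clinical recording, could leave a gap. The resting-state description is also written around fitting a cap, and may not govern segments drawn from clinical recordings. Likewise, the baseline EEG is free of earlier testing only as far as the listed steps of that cycle go. All this stands, but the plan guarantees no interval and gives no segment rule.

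*Matching the order does not isolate LIFUP.* Correct. Two fMRI blocks, elapsed time and the lack of a sham or control cycle remain. That is a reason not to oversell the change. It is not a reason to keep a difference that can be avoided.

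*The CRS-R deserves priority after LIFUP.* It carries Aim 1 and H2, and the Neurobehavioral Assessment Procedure section wants it done straight after exposure. This stands, and it decides which side of the sequence to change.

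**Conclusion.** The point holds as a minor one. The order is unmatched on the face of the Procedure section, and nothing in the EEG analysis separates an effect of the preceding CRS-R from an effect of LIFUP. The pre/post spectral comparison may therefore be confounded. The timing is 0 to 20 min after a CRS-R for the second recording, against no CRS-R earlier in the cycle for the first. The resulting bias, if any, cannot be sized from the documents.

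This rests on reading the 25 min clinical measures as the CRS-R, on the listed durations without transport, and on the assumed set-up range.

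It would be wrong to conclude that the main results are compromised. The EEG appears in neither Aims 1-2 nor H1-H3, and the CRS-R and BOLD comparisons do not use it. It would be equally wrong to conclude that a matched order makes a spectral change attributable to LIFUP alone.

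**What to change.** Take the baseline EEG segment after the baseline CRS-R, and set the same CRS-R-to-EEG interval on both sides. State this order and interval in the Procedure list and in the Electroencephalography item, with the rule for choosing the 10 min segment. In the same item, say that the comparison is uncontrolled and that scanning and elapsed time still differ between the two recordings.

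Cost: no extra recordings or staff, and the CRS-R after LIFUP keeps its planned timing. As the data come from clinical recordings, the change may amount to choosing a different segment. The small downside is that the baseline EEG is no longer recorded before all testing.

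Moving the post-LIFUP EEG ahead of the post-LIFUP CRS-R is the less attractive alternative, because it delays the behavioural outcome by 10 to 30 min for the sake of a supplementary measure.

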- **Change in CRS-R related to LIFUP.** *Maximum CRS-R score prior to LIFUP will be compared to the maximum CRS-R score following LIFUP.* Behavioral responsiveness in patients was assessed using the total score on the CRS-R. Prior to analysis, the highest CRS-R prior-to and following LIFUP exposure will be calculated in order to best capture patients' maximal performance. A matched samples T-test analysis will be performed. Where a violation of normality is detected (using a Shapiro-Wilk test) a non-parametric Wilcoxon signed rank test will be used to compare Pre-LIFUP and Post-LIFUP scores for all patients.

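### The CRS-R test compares best score before with best score after LIFUP without equalising the number of scores or classifying scores between two exposures, so testing frequency alone can produce a change

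*Combined protocol and SAP*

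**What the plan says.** Under Statistical Plan and Analysis, the CRS-R item states that "Maximum CRS-R score prior to LIFUP will be compared to the maximum CRS-R score following LIFUP". For each patient "the highest CRS-R prior-to and following LIFUP exposure will be calculated", with the aim of capturing best performance. Then "A matched samples T-test analysis will be performed", replaced by a Wilcoxon signed rank test if Shapiro-Wilk detects non-normality. The item gives no number of scores per side, no time window and no matching of counts.

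The schedule has to be pieced together from three places:

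- Neurobehavioral Assessment Procedure: "Baseline responsiveness will be assessed prior to LIFUP exposure", with no number. Afterwards, "Responsiveness will also be assessed immediately following, as well as on the days following each LIFUP exposure", again with no number.
- Procedure, introduced by "The temporal sequence of events, for each cycle, is as follows": one baseline and one post-LIFUP clinical collection per cycle. The later-day assessments are not listed, so this is not a full CRS-R schedule.
- Inclusion Criteria: both patient groups need a "Behavioral profile consistent with a VS or MCS as assessed with the Coma Recovery Scale Revised". Whether that eligibility score counts as a pre score is not stated.

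The BOLD item shows that some patients have two exposures and averages their two runs. The CRS-R item has no corresponding rule.

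**The concern.** There are two gaps.

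**Unequal counts.** If a patient's score fluctuates from test to test, the highest of three scores is on average higher than the highest of one or two. Wanting to capture best performance justifies using a maximum. It does not justify giving one side more chances to reach it.

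**Scores between exposures.** In a two-exposure patient, scores taken after the first exposure, and the second cycle's baseline, come both after and before LIFUP. No rule assigns them, and the choice can change the size and even the sign of the result.

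This is the only analysis of a behavioural measure in the statistical plan. The preliminary-efficacy part of Aim 1 rests on it, as does the claim in H2 that arousal or awareness improves. With unequal counts, part of the reported change and of its significance would reflect how often patients were tested.

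**Working it through.** The plan gives no sample size, power or CRS-R significance level, so there is no figure to reproduce. The check asks what the planned comparison yields when LIFUP has no effect.

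**Counts (inferred).** Pre: one baseline in the cycle list, or two if the eligibility CRS-R counts. Post: one immediate score plus an unstated number on later days; two later days are assumed, giving three.

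**Other assumptions, none in the documents.** Normal scores, within-patient SD of 1 to 3 points, two-sided 5% paired t-test, n = 6, 10 or 20.

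**Bias with independent scores.** False change = SD × [E(max of k post) − E(max of k pre)]. For standard normal scores, E(max) is 0, 0.564, 0.846, 1.029, 1.163, 1.267 and 1.352 for k = 1 to 7. At SD 2:

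- 2 pre vs 2 post: 0
- 2 vs 3: 2 × (0.846 − 0.564) = +0.56
- 1 vs 3: 2 × 0.846 = +1.69
- 3 vs 2: −0.56

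The bias is proportional to the SD: for SD 1 to 3 it is +0.28 to +0.85 (2 vs 3) and +0.85 to +2.54 (1 vs 3).

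**Bias with correlated scores.** Take lag-1 correlation 0.8, hence 0.64 at lag 2. E(max of 2) = √((1 − 0.8)/π) = 0.252. E(max of 3) = [√0.4 + √0.4 + √0.72] / (2√(2π)) = 2.113/5.013 = 0.422. At SD 2 this gives 2 × (0.422 − 0.252) = +0.34 for 2 vs 3 and 2 × 0.422 = +0.84 for 1 vs 3.

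**False-positive rates**, simulated with 20,000 trials per cell. 'Change SD' is patient-to-patient variation in true change around a mean of zero.

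| Assumptions | 2 vs 3: bias; rate at n = 6/10/20 | 1 vs 3: bias; rate at n = 6/10/20 |
|---|---|---|
| SD 2, independent, change SD 0 | +0.56; 8/11/19% | +1.69; 27/48/82% |
| SD 2, correlation 0.8, change SD 0 | +0.34; 7/9/14% | +0.84; 18/33/66% |
| SD 2, independent, change SD 3 | +0.56; 6/7/10% | +1.69; 14/23/45% |
| SD 2, correlation 0.8, change SD 3 | +0.34; 5/6/7% | +0.84; 8/11/18% |
| SD 1, correlation 0.8, change SD 3 | +0.17; 5/5/6% | +0.42; 6/7/9% |

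Equal counts (2 vs 2) reject about 5% in every row. Applying the plan's Shapiro-Wilk and Wilcoxon rule leaves the top row almost unchanged: 8/11/19% and 26/48/82%.

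**Two exposures.** Assume two pre scores, three post, a second baseline and three more post, independent, SD 2. The true-gain column assumes a lasting 2-point gain from the first exposure.

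| Rule for pre | Counts | No effect | True lasting gain of 2 |
|---|---|---|---|
| Everything before the first exposure | 2 vs 7 | 2 × (1.352 − 0.564) = +1.58 | +3.6 |
| Each cycle's baseline | 3 vs 6 | 2 × (1.267 − 0.846) = +0.84 | +1.9 |
| Everything before the last exposure | 6 vs 3 | −0.84 | −0.5 |

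If only half the patients have two exposures, averaging with the single-exposure +0.56 gives +1.07, +0.70 and −0.14.

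**The case against.** **The imbalance is inferred.** A reader might conclude that the plan prescribes more post than pre scores and so builds in a gain for LIFUP. The documents do not say that. The only itemised sequence shows one collection before and one after, nothing rules out repeated baselines, and speaking of a highest pre score suggests more than one. This stands. However, the later-day assessments are required after every exposure and nothing comparable is required before, so more post scores remains the most plausible reading.

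**The large error rates are not established.** A reader might take 82% as the expected false-positive rate. It needs one pre score, three independent post scores, 20 patients and no variation in change. Correlation and variation together bring the rates close to nominal, and no CRS-R significance level is stated. Whole-point scoring also matters if patients barely fluctuate: at SD 0.3, 2 vs 3 rejects about 1/4/10%. This too stands; the rates show a range, not an estimate.

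**The sign reversal is not general.** It arises under one classification rule, and with half the patients re-exposed it almost vanishes (−0.14; rejection 4/4/5%). What remains is that the plan does not choose a rule.

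**The study is small and uncontrolled.** Natural recovery, notably in patients under six weeks from injury, is mixed in whatever summary is used, and a pre/post test cannot address the comparison with DBS in H2. That limits what any correction achieves. It does not justify leaving in an artefact that wording can remove.

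**Best performance is a deliberate target.** Replacing it with means changes what is measured and could dilute a brief effect. This is a fair reason to keep a maximum, over equal counts.

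**Conclusion.** The point holds as a conditional one and should be fixed. It is certain from the text that the plan compares two maxima without equalising counts, defining windows or classifying scores between exposures. It is certain by arithmetic that unequal counts shift the mean change when LIFUP does nothing: upwards with more post scores, downwards with more pre scores, and not at all with equal counts. That post scores outnumber pre scores is an inference from the schedule.

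The size is illustrative. At SD 2 the false gain is +0.34 to +0.56 points (2 vs 3) or +0.84 to +1.69 (1 vs 3), for lag-1 correlation 0.8 down to 0. False-positive rates at n = 6/10/20 run from about 5/5/6% to 8/11/19% (2 vs 3) and from 6/7/9% to 27/48/82% (1 vs 3). SD, correlation, variation in change, counts, n and significance level are all assumptions. A reader might infer that correcting this would isolate the LIFUP effect. It would not, because no control group is described.

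**What to change.** Amend the CRS-R item of Statistical Plan and Analysis:

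1. Define pre as all CRS-R scores before the patient's first exposure. State whether the eligibility CRS-R counts and how many later-day scores are scheduled. Class every later score, including the second cycle's baseline, as post.
2. Keep the best-performance measure, but test the maximum over k pre scores against the maximum over the first k scheduled post scores. Report the maximum over unequal counts as descriptive only, with the counts.
3. As an alternative or sensitivity analysis, test each patient's mean post minus mean pre over all scores, with the same paired t-test or Wilcoxon rule. The expected mean does not depend on the number of scores. Rule 1 is still needed: for a true lasting 2-point gain in the two-exposure example, means report 2.0, 1.33 or 0.67 under the three classifications.

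With no effect, both measures rejected 4.4% to 5.4% in every simulated case.

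**Cost.** SAP wording and a little code; no new assessments. The matched maximum drops post scores beyond k and usually everything after a second exposure; with k = 1 only the immediate score remains. Means give up the focus on best performance. Reported gains will be smaller than with the unequal maximum.

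Power for a true 2-point gain (SD 2, independent scores, n = 6/10/20) is 40/67/95% for the matched maximum and 58/87/99% for means with 2 vs 3 scores, and 29/52/85% and 40/68/95% with 1 vs 3. At lag-1 correlation 0.8 and n = 6/10, the advantage of means disappears for 2 vs 3 (73/96% matched, 74/96% means) and reverses for 1 vs 3 (87/99% matched, 77/97% means).

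### The same-day post-LIFUP CRS-R follows 110 minutes in the MRI suite that no baseline score follows, and the highest-score rule keeps a temporary rise but mostly replaces a temporary drop

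*Combined protocol and SAP*

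**What the plan says.** The Procedure section sets the order of events in each cycle. After the baseline EEG comes the behavioural baseline, "Baseline clinical measures collection (25 min". Three blocks in the MRI suite follow: "Baseline fMRI measures collection (in MRI suite; 30 min+20 min set-up", then "Administration of LIFUP (in MRI suite; 10 min + 20 min set-up", then "Post-LIFUP fMRI measures collection (in MRI suite; 30 min". Only then is the patient tested again: "Post-LIFUP clinical measures collection (25 min". The LIFU Procedure paragraph adds positioning scans whose number is not fixed, "re-acquiring a T1-weighted MPRAGE at each iteration".

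The Neurobehavioral Assessment Procedure section makes clear that there is more than one post-LIFUP score: "Responsiveness will also be assessed immediately following, as well as on the days following each LIFUP exposure". It does not state how many assessments are made before or after LIFUP.

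Under Statistical Plan and Analysis, the CRS-R item reduces each side to one number, "the highest CRS-R prior-to and following LIFUP exposure will be calculated", so as to reflect each patient's best performance. The two maxima are compared with a paired t-test, or with a Wilcoxon signed rank test if normality fails. The CRS-R plan describes no sham session, scan-only session or adjustment for the scan session.

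**The concern.** One of the post-LIFUP scores is taken under a condition that no baseline score in the cycle shares: directly after a long period of transport, strapping, positioning and scanning. Any short-lived effect of that session on responsiveness is mixed with the effect of sonication.

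The maximum rule makes this one-sided. A raised same-day score is likely to be the highest and becomes the patient's result. A lowered one is likely to be overtaken by a following-day score and drops out. Session effects that average zero across patients would therefore still give a positive mean change, and equal numbers of pre and post assessments would not prevent it.

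CRS-R change is the main clinical evidence for Aim 1 and for H2, and H2 is stated in terms of arousal and/or awareness, so a change in arousal from another source bears directly on the claim.

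**Working it through.** **Time between the two same-day tests** (Procedure section): (30 + 20) + (10 + 20) + 30 = 110 minutes in the MRI suite. Sonication is 10 of these. The other 100 are scanning and set-up, before any repeat positioning scans.

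**Why the maximum is asymmetric.** The plan gives no sample size, SD or number of assessments, so there is no figure of its own to reproduce, and everything below is assumed. Take two independent normal scores on each side with within-patient SD s, no LIFUP effect, and a session shift d on the same-day post score only. With θ = s√2,

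expected post maximum = d·Φ(d/θ) + θ·φ(d/θ), and expected pre maximum = s/√π.

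- s = 2, d = +2: θ = 2.828 and d/θ = 0.707, so 2 × 0.7602 + 2.828 × 0.3107 = 2.399. Less 1.128, the change is +1.27.
- s = 2, d = -2: -2 × 0.2398 + 0.8787 = 0.399. Less 1.128, the change is -0.73.
- An equal mix of the two: (1.27 - 0.73)/2 = +0.27, although the mean shift is zero.
- s = 1.5: 2 × 0.8271 + 2.121 × 0.2558 - 0.846 = +1.35 and -2 × 0.1729 + 0.5426 - 0.846 = -0.65. The equal mix gives +0.35.

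With a single post score, the changes would be +d and -d and the mix would give zero. The asymmetry needs two or more post scores, which the assessment schedule implies.

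**Effect on the test.** Simulation of 20,000 trials with n = 12, 2 to 4 scores on each side in equal numbers, s = 1.5 or 2, no LIFUP effect, and a two-sided 5% paired t-test:

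| Session shift on the same-day score | Mean change (points) | Rejection rate |
|---|---|---|
| None | about 0 | about 5% |
| +2 or -2 with equal chance | +0.24 to +0.35 | 6-9% |
| +2 in one third of patients | +0.26 to +0.45 | 7-11% |
| +2 in every patient | +0.8 to +1.4 | 23-65% |
| -2 in every patient | -0.25 to -0.73 | rejections are against LIFUP |

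**Sensitivity.** The size depends on the shift relative to s. With s = 2 and shifts of +1 or -1 in equal mix, the bias is only +0.06 to +0.07. With s = 1 and shifts of +2 or -2 in equal mix, it is about +0.5. In that last case, with three scores on each side and n = 16, 25% of trials reject in favour of LIFUP against a nominal 2.5%.

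**Dropping the same-day score without other changes.** Starting from k scores on each side, this leaves k pre against k - 1 post. With no LIFUP effect and no session effect, for s = 1.5 / s = 2:

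- 2 pre, 1 post: mean change -0.85 / -1.13 (exactly -s/√π), rejection about 27-28%.
- 3 pre, 2 post: about -0.42 / -0.57, about 13%.
- 4 pre, 3 post: about -0.28 / -0.37, 8-9%.

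Nearly all of these rejections are against LIFUP. With equal counts on both sides, the rate returns to about 5%.

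**The case against.** The strongest objection is that the session effect is postulated. Nothing in the documents says that scanning rouses or tires these patients. A reader might infer that scan arousal does inflate the CRS-R result, or that a positive result would be an artefact of scanning. The documents do not support either. They support only the conditional statement: if such an effect occurs, it cannot be told apart from LIFUP, and the chosen summary favours rises over drops. This objection stands and limits the point.

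Second, the high false-positive rates need a consistent +2 points in every patient, which is an extreme case. In the milder rows of the table the rate is 6-11%. The model also shifts one score only, whereas the plan allows repeated exposures and does not say whether scores taken between exposures count as pre or post. This stands too.

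Third, the confounding comes from the uncontrolled pre/post design. With one post score and no maximum, a session shift would pass through in full. That is correct, and a label on the same-day comparison does not remove it. The maximum rule adds the asymmetry, and the pooling hides which score produced the gain. Both can be changed without a control arm.

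Fourth, relying on later days could admit more spontaneous recovery, especially in acute patients less than 6 weeks from injury. The following-day scores are already in the planned maximum, however, so this exposure is not new, and removing a score can never raise a patient's post-LIFUP maximum. Recovery remains a limit of any version of this analysis.

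Finally, the study is a small feasibility study of preliminary efficacy. That argues for a cheap change in the analysis, not for a redesign.

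**Conclusion.** The point holds in conditional form. The order of assessments, the 110 minutes and the highest-score rule are all in the text, and the asymmetry follows from taking a maximum over two or more post scores. Whether a session effect exists, and how large it is, cannot be learned from the documents.

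Under assumed +2 or -2 point shifts of mean zero, with n = 12, within-patient SD 1.5-2 and equal counts of 2 to 4 scores, the bias is about +0.25 to +0.35 points with a false-positive rate of about 6-9%. Under those settings it becomes much larger only if most patients shift upward. It is negligible for shifts that are small relative to the SD, and larger if the SD is nearer 1 point. It would be wrong to conclude that the plan has a known false-positive rate of 23-65%.

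This is a worthwhile, low-cost improvement, not a flaw that invalidates the study.

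**What to change.** In the CRS-R item of the Statistical Plan and Analysis, replace the single maximum-against-maximum test with two prespecified paired comparisons:

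- (a) Following-day bedside scores against pre-LIFUP scores, using the same number of assessments on each side, or a summary whose expected value does not depend on the number, such as the mean. The matching is essential, because removing the same-day score from a maximum without it creates the downward bias shown above.
- (b) The same-day post-LIFUP score against that day's baseline, labelled as including any effect of the MRI session.

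State in advance that a gain seen only in (b) will not be attributed to LIFUP alone. For patients with two exposures, state which scores count as pre and which as post. The Neurobehavioral Assessment Procedure section places a CRS-R directly after LIFUP, while the Procedure section puts a 30-minute fMRI block in between; the two should be reconciled.

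The cost is SAP wording and one extra paired comparison on data already collected. The downside is that an effect that fades within a day appears only in (b). Comparison (a) assumes that no session effect carries over to the next day, and neither comparison removes spontaneous recovery.
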